2.2.2 Known Potential Benefits

As with all medications, over the counter and prescription remedies for tension headaches may have undesirable side effects. Additionally, these products are known to contain additives, dyes, fillers and other unnatural or synthetic ingredients that consumers are looking to avoid. As such, these consumers are seeking natural, plant-based alternatives for symptom relief. Research participants may benefit from the intervention by eliminating such unwanted side effects when treating their symptoms of pain and/or tension headache while achieving symptom relief. If the intervention is shown to be efficacious, this would provide a viable prevention option for others in the general population to decrease their need for drugs that contain undesired ingredients. Other benefits include detailed surveillance of symptoms and documentation of activities, routine medications and supplements that may provide participants and their regular physician or other healthcare provider with useful information for diagnosis and treatment of symptoms should they occur.

2.2.3 Minimization of Risks

Research participants will be carefully screened to meet enrollment criteria. Participants meeting exclusion criteria will not be enrolled. The study participant informed consent will be presented with clear description of the study requirements and opportunity to have questions answered before enrollment. Once an event occurs review of symptoms will be ascertained at 15 and 30 minutes for up to an hour. Reporting of adverse events will be reviewed routinely and in accordance with regulatory guidelines (21CFR, GCP) by the Principal Investigator. Participants with occurrence of worsening symptoms or adverse events should stop taking the test product and may seek medical attention and exit the study.

3 Study Objectives

Beyond the obvious physical symptoms, lifestyle impact related to tension headaches include decreased work productivity and lost work time [17, 18]. The purpose of the present study is to 1) evaluate the impact of the tension relief test product on the symptoms of tension headaches and functional status in adult men and women who suffer from mild to moderate tension headaches by using the 10-point Mankoski scale [19] and 2) the

subjective experience of these participants related to general health, symptoms of tension headaches, and personal experience with the products.

This will be evaluated based on the primary and secondary endpoints. These endpoints, the analysis populations, and their respective measures are described below. Further details on the methods for measuring the outcomes can be found in the Study Outcome Measures and Analysis Plan sections.

Primary Endpoint:

The primary endpoint is reduction in tension headache severity. Patients will be asked to rate headache on the 10-point Mankoski scale at 4 time points: prior to taking the product, 15 minutes after taking the product, 30 minutes after taking the product and 1 hour after taking the product. The improvement in symptoms from baseline will be evaluated on a pairwise basis separately for each time point. P-values will be computed for the improvement.

There is no control group for the primary analysis.

Secondary Endpoints:

- The time to other intervention will be analyzed.
- A longitudinal analysis will be performed for patients who report on more than one incident of headache.
- Comparison against the participant's normal behavior.
- Net Promoter Score.
- Adverse events will be summarized.
- An additional data presentation will consist of results from both Treatment and Control
 in similar studies appearing in the literature. There will be no formal statistical
 comparison of results from this study and historical studies.

4 Study Design

The present study will be a prospective, one arm observational study. Patients will begin taking the capsules at the onset of headache symptoms. Onset is defined as the time the participant takes the test product for relief of symptoms. When the participant decides to take the test product, they will report symptoms in the headache diary immediately before to taking the product and rate their symptoms on a 10-point Mankoski scale. After consuming the product, the participant will complete a Mankoski scale at 15 minutes, 30 minutes and 1 hour after taking the product. If needed the participant will be allowed to take alternative medication (alternative treatment) after an hour after taking the product. If alternative medication is taken, the participant will record this in their headache diary.

Study enrollment and management will be de-centralized, where participants do not visit an investigator or a clinic for clinical assessment. The participants will participate in the study at home.

All data collected from during this study will be reported by the patient via eCRFs, eDiary, and other electronic data entries. If a visit is required, it will be conducted via remote contact by telephone.

4.1 Test Product

Below are descriptions of the test products and their ingredients.

Tension Relief Product

Description: Combining Boswellia, Magnesium, Feverfew, Skullcap and White Willow Bark for multi-faceted effective, yet health-building head comfort. This formula is designed to promote comfort of the head and body in the short-term.

Active Ingredients: Magnesium (as Magnesium glycinate), Boswellia (40% Boswellic acids), White Willow Bark (15%Salicin), Skullcap, Feverfew.

Inactive Ingredients: Vegetarian capsule (vegetable cellulose, water) Rice Hull Concentrate.

4.2 Required Behavior

During the 1 hour after taking the test product, no medication or supplementation (including all CBD products) other than the test product should be taken. Once the 1-hour report has been submitted the patient may take other medications.

Patients are asked to limit the consumption of alcohol beverages to less than or equal to two drinks per day and to abstain from the use of cannabis for the duration of the study.

4.3 Participation Period

Participants are expected to participate in the study for 60 days after study start. The product may be used after each onset of tension headache, but not more often than three times per day. Patients will be discontinued from the study 60 days after study start or after three recorded headache episodes. Study start is defined as the day the participant received the test product and completed the receipt of test product form.

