- After completing the surveys, the participant will take test product. The participant will take 2 capsules with 6-8 oz. of water per headache episode. With a max of 6 pills per day. (If participant takes 6 pills in 1 day this will be defined as 3 headache episodes and the patient will be exited from the study).
- After taking the test product, the participant will complete a Mankoski pain scale at 15 minutes, 30 minutes, and 1 hour after taking the test product.
- Once the participant's symptoms resolve, the participant will complete the headache diary.
- If the participant takes any other medication outside of the test product, the participant will record this on the headache diary.
- After taking the test product, the participant will be instructed to fill out an Adverse Event form for any side-effects experienced.
- After the first headache episode, the participant will be asked to complete the same process for another 2 headache episodes; however, these are not required.
- If the participant completes the required assessments for a total of 3 headache episodes, they will be prompted, by email, to exit the study.

- If the participant only completes the required assessments for the required 1 headache episode, the participant will be prompted, by email, to complete the study exit form and will be exited from the study on day 60 (60 days from the day of receipt of the test product).
- The sponsor nor Hawthorne Effect Inc. will not make any attempt to collect any unused product.
- Upon receipt of study exit survey and review of completed study forms, participant will receive an Amazon gift card of \$25 via email.

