6.4.1 Anticipated Adverse Events

Anticipated Adverse Events are complications that are known to be associated with the test product (in high doses exceeding recommended use):

- Diarrhea
- Nausea
- Stomach Cramps
- Acid Reflux
- Skin Rashes
- GI Bleeding
- Headaches
- Liver Damage

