6.6 Test Product Packaging/Handling/Storage/Accountability

- The three-episode supply of test product will be packaged and labeled with ingredients and a study ID number.
- Participants will receive guidance on how to report receipt, store, and use the test product.
- Hawthorne Effect Inc. will support storage and shipment of test product, documentation of test product assignment, and completion of test product accountability.

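### No minimum adverse event (AE) observation after the last dose is defined: exit follows the third episode or day 60, the exit AE assessment is undated relative to dosing, and delayed events can go uncollected

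*Combined protocol and SAP*

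**What the plan says.** Participation ends at whichever comes first: "Patients will be discontinued from the study 60 days after study start or after three recorded headache episodes" (section 4.3). Section 6.1 gives the mechanism. Each episode uses one dose: "The participant will take 2 capsules with 6-8 oz. of water per headache episode". On reaching the limit: "If the participant completes the required assessments for a total of 3 headache episodes, they will be prompted, by email, to exit the study". A separate rule covers heavy same-day use: "If participant takes 6 pills in 1 day this will be defined as 3 headache episodes and the patient will be exited from the study". A participant with only one completed episode "will be exited from the study on day 60 (60 days from the day of receipt of the test product"). Two-episode participants are not named in section 6.1, but the day-60 rule in section 4.3 covers them. Section 6.6 limits the supply: "The three-episode supply of test product will be packaged and labeled with ingredients and a study ID number".

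The schedule of activities (section 6.2) marks an AE assessment at each event, at 15, 30 and 60 minutes after it, and once more at study exit. The exit column carries no day and no interval from the last dose. Two instruments have no time limit: the diary's side-effect question (Appendix E), completed after the headache resolves, and the AE form (Appendix G), which asks how long after the dose the effect began.

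Section 6.4.1 introduces its list of expected events with "Anticipated Adverse Events are complications that are known to be associated with the test product (in high doses exceeding recommended use"). The list includes GI bleeding, skin rashes and liver damage. Appendix G also asks about yellowing of skin or eyes and dark urine. Section 6.4 says that participants with an AE will be advised to stop the product.

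**The concern.** The plan looks for kinds of event that can take days to appear, but the only safety observation it guarantees after a given dose is 60 minutes. Everything later depends on when the exit form happens to be completed. For a three-episode participant that moment follows an emailed prompt, and the gift card is released only after the exit survey is received and the forms reviewed (section 6.1), which is a reason to answer soon. For everyone else it depends on how close to day 60 the last dose fell.

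AEs are listed for summary among the secondary endpoints (section 3). Section 2.2.1 supports the minimal-risk determination partly by saying that the listed side effects were seen at doses well above the recommended one, alongside the regulatory status of the ingredients. The AE summary is this trial's own evidence on that statement. If late events have no defined route into the data, a low count cannot be told apart from a short look.

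**Working it through.** The plan states no length of safety observation after the last dose, so there is no figure to reproduce. The check asks how many participants are affected, and by how much, under the plan's own planning rate and a range around it.

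**Inputs**
- 50% of participants have a headache within 60 days (section 7.2).
- 97 treated participants desired (section 5.1).
- Three episodes × 2 capsules = 6 capsules, the full supply (sections 6.1 and 6.6).
- Exit at the earlier of day 60 and the third episode (section 4.3).
- Assumed: episodes occur at one constant rate for all participants, each treated with one dose. Section 5.1 uses a constant hazard for its own forecast of treated participants.
- Assumed: three-episode exit is placed 1 hour after the third dose, the last timed assessment. Actual exit may be later.

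**Step 1, rate.** 1 − exp(−60λ) = 0.5, so 60λ = ln 2 = 0.693.

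**Step 2, episodes per treated participant (Poisson, mean 0.693).**
- P(1) = 0.5 × 0.693 = 0.3466
- P(2) = 0.5 × 0.693² / 2 = 0.1201
- P(3 or more) = 1 − 0.5 − 0.3466 − 0.1201 = 0.0333
- Divided by the 0.5 who are treated: 69.3%, 24.0% and 6.7%
- Three-episode participants among 97: 97 × 0.0666 = 6.46, about 6

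**Step 3, time from last dose to exit.**
- One episode: uniform over 60 days. Median 30 days; P(under 7 days) = 7/60 = 11.7%.
- Two episodes: P(gap under g days) = 1 − (1 − g/60)². Median 60 × (1 − √0.5) = 17.6 days; P(under 7 days) = 1 − (53/60)² = 22.0%.
- Three episodes: 1 hour guaranteed, then an undated exit form.

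Seven days is a yardstick for illustration only.

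**Step 4, who shares the gap at the planning rate.**
- Late dosers with one or two episodes: 0.693 × 0.117 + 0.240 × 0.220 = 0.081 + 0.053 = 0.134 of treated participants, about 13 of 97.
- Three-episode participants: 0.067, about 6 of 97.

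The gap is therefore close to certain for a prompt three-episode exit, yet at this rate more of the affected participants have had one or two episodes.

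**Step 5, time from first dose to exit (simulated medians, planning rate).** One episode 30 days, two episodes 42 days, three episodes 29 days.

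**Step 6, range for three-episode participants (simulated).** The monthly rates are assumptions, with 30.4 days to a month.

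| Rate | Share of treated reaching three | Median exit day | Median days, first dose to exit | Median days, third dose to day 60 |
|---|---|---|---|---|
| 50% in 60 days (plan) | 6.7% | 46 | 29 | 14 |
| 1 per month | 37% | 42 | 26 | 18 |
| 3 per month | 94% | 26 | 16 | 34 |
| 4.3 per month | 99% | 19 | 12 | 41 |

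One-episode medians from first dose stay at about 30 days at every rate. The last column shows what holding AE collection open to day 60 would add after the third dose.

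**The case against.** The strongest reply is that AE collection does not stop at the third dose. An AE assessment is scheduled at exit, the diary question comes after the headache resolves, the AE form has no time limit, and exit follows a prompt whose timing the plan does not fix. This stands: the interval is undefined, not zero, and events before the exit form is completed can be captured.

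A reader might also infer that full-supply users have the shortest safety observation. That depends on the measure. It is true from study start when the third episode precedes day 60, and on average after the last dose. From first dose, at the planning rate, the medians are 29 days against 30 for one episode. The difference widens only at the higher assumed rates.

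A reader might go further and expect the AE summary to show a false inverse dose relation across 2, 4 and 6 capsules, or a bias at the highest labelled daily intake. The documents plan no comparison by capsules taken: section 3 says AEs will be summarized, and section 7.3 confines formal group comparisons to covariate analyses. Three episodes usually means 2 capsules on each of three occasions; only the 6-in-one-day case reaches the daily maximum. Any such comparison would be confounded anyway, because participants with an AE are advised to stop and so are less likely to reach three episodes.

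Finally, the public text of Appendix H breaks off and the consent pages are not available, so a late-reporting instruction to participants cannot be excluded. That limits certainty. It would not supply the missing interval in the schedule, which is the controlling text.

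**Conclusion.** The concern holds in a limited form. The plan sets no minimum AE observation after the last dose for any treated participant, gives the exit AE assessment no timing relative to dosing, and describes no AE contact after exit. Delayed events of the kinds it anticipates can go uncollected. To say that they are missed would be too strong, because the documents give neither a rate nor a latency for such events.

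At the planning rate about 6.7% of treated participants (about 6 of 97) reach three episodes and may have little more than the 60-minute check. A further 13% or so dose within 7 days of day 60. If headaches are more frequent than planned, the three-episode group becomes the majority: 37% at one a month, 94% at three. These figures rest on a constant rate common to all participants, one dose per episode and prompt exit after the third; the gap itself does not depend on them. The primary efficacy analysis is unaffected. The point should be settled before enrolment, because events not asked about cannot be recovered at analysis.

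**What to change.** Separate the end of dosing and diaries from the end of AE collection. Leave the three-episode limit, the dosing and the diaries unchanged. Send every treated participant one automated Appendix G form at the same pre-stated interval after the last dose, even if this falls after exit or day 60. The sponsor and investigator should choose the interval from the events they anticipate and state it in sections 4.3 and 6.1, with a matching column in the section 6.2 schedule.

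Extending AE collection to day 60 for everyone is not enough: a dose on day 59 would still leave one day, and at the planning rate the median after a third dose would be about 14 days against 30 for one-episode participants.

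In the analysis plan, report AEs with the number of treated participants who answered the form and the observed time since last dose. State that counts by capsules taken will not be read as a dose relation, because participants with AEs are advised to stop.

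The cost is a protocol sentence, a schedule column, one automated form and a line telling participants to expect it. Some will not answer, and contact lasts slightly longer. The text should say that the alcohol and cannabis limits (section 4.2) and the gift card (section 6.1) remain tied to the existing exit, and whether non-response to this form triggers the contact steps in section 6.5.

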4.4 Data Collection

All data in the present study will be self-reported by the participant and collected via their online portal (Hawthorne Effect Study Visit Management System (HE VMS)). Participants will be asked to take the test product according to the instructions for use, complete study surveys and respond to study reminders during the course of the study. The instructions for use and study forms can be found in the appendix. (*Appendices B, D, E, F, G*)

5 Study Population

5.1 Selection of the study Population

The study population will consist of at least 200 adult patients who suffer from symptoms of tension headaches and who have completed the self-enrollment form and who meet the inclusion-exclusion criterion. The participants will otherwise be in good health.

The target sample size for this study is initially 200 participants, with a desired sample of 97 treated participants. This is described in detail in the Statistical Considerations section.

At such time as 180 participants have been enrolled, the available data will be analyzed using a constant hazard model to determine if it seems realistic that the desired number of 97 treated patients will be met by the end of follow-up. If the expected number of treated patients is less than 97, the target sample size will be increased as needed, considering both the desire for 97 treated participants and the timelines of the trial sponsor. The actual outcomes of treated participants will not be considered in this analysis, merely whether or not enrolled participants have reported starting using the test product.

Enrollment will be stopped once 200 patients have been enrolled, no further patients will be offered a place in the trial once the target sample size criteria has been met. All patients who have already been offered places, but who have not yet consented, will be allowed to participate as long as they have signed the study consent within 15 days and the total number of participants does not exceed 125% of the target (either 200 or the recomputed target if recomputation has been performed).

In order to ensure an age and sex distribution that is reasonably representative of the US population, enrollment may be stopped early in some age and sex groups.

Target population for this study are candidates who suffer from mild to moderate tension headaches.

Participants will be enrolled from across the United States. No participants will be enrolled outside of the United States. It is expected that the geographical distribution of the participants enrolled in the study will correlate with the geographical distribution of the general population across the United States.

Participants will be recruited via digital advertisements and social media.

After clicking on an advertisement, potential participants will then be directed to a website where they will complete a screening questionnaire (See *Appendix C*). The screening questionnaire will automatically qualify or disqualify them for study participation. If the participant qualifies, they will be provided an informed consent. Upon completion of the informed consent they will be deemed enrolled in the study.

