7.1 Study Outcomes Measures

Analysis populations:

The *intent to treat* (ITT) population consists of all participants who are consented, report the onset of a headache, and have taken the study medication at least once. The primary analysis will be in the ITT population.

Primary Endpoint:

The primary endpoint is reduction in headache severity. Patients will be asked to rate headache on the 10-point Mankoski scale at 4 time points: prior to taking the product, 15 minutes after taking the product, 30 minutes after taking the product, and 1 hour after taking the product. The improvement in symptoms from baseline will be evaluated on a pairwise basis separately for each time point. P-values will be computed for the improvement.

There is no control group for the primary analysis.

Secondary Endpoints:

- Time to intervention (taking any product other than the study medication) will be analyzed as a time dependent variable, with the clock starting when the test product is taken.
- A longitudinal analysis will be performed for patients who report on more than one incident of headache.
- Net Promoter Score.
- Comparison against normal behavior will use the paired sample *t*-test.
- An additional data presentation will consist of results from both Treatment and Control

in similar studies appearing in the literature. There will be no formal statistical comparison of results from this study and historical studies.

Secondary endpoints will be gathered on the subjective experience of these participants related to general health, personal experience with the product. The secondary endpoints will be self-reported by the participant on their online portal. There will be a questionnaire related to general health and the subjective experience of the participant administered at baseline and at study exit.

The purpose of the secondary analyses is to investigate the association between various baseline and other measurements and outcomes. These secondary analyses are considered hypothesis generating, and the descriptions are somewhat informal. The trial data may suggest secondary analyses not described here.

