7.2 Sample Size Considerations

Based on information from a variety of studies, a highly pessimistic assumption is that there would be a mean improvement of 2 points on the Mankoski scale with a standard deviation of 5 points. Based on these assumptions, a sample size of 68 patients would result in a 90% power to detect an improvement using the paired-sample *t*-test. We also assume that 50% of the patients will experience headaches during the 60-day period; the other patients would furnish no useful data. The final sample size of 200 patients has been chosen to allow for various contingencies, including uncertainties in the assumptions and about compliance in this self-reported trial. If data from multiple headaches per patient are useful, the power to detect an improvement would increase.

It should be emphasized that these assumptions are for sample size purposes only. Trial analysis will use the data as collected.

As discussed above, the number 200 may be increased based on observed data concerning the number of participants with heartburn/indigestion. The actual outcomes of treated participants will not be considered in this analysis, merely whether or not enrolled participants have reported starting using the test product. The method of reevaluating the sample size will be described in the Statistical Analysis Plan.

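### Does the plan need changing because Section 7 never derives the 97 treated participants that Section 5.1 says it describes?

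*Combined protocol and SAP*

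**What the plan says.** Section 5.1 gives an initial enrolment target of 200, "with a desired sample of 97 treated participants. This is described in detail in the Statistical Considerations section". The number 97 appears four times in that section, always in the same role. Once 180 participants are enrolled, a constant hazard model projects how many will have used the product by the end of follow-up. The rule is then: "If the expected number of treated patients is less than 97, the target sample size will be increased as needed". How far it rises is a judgement that sets the aim of 97 against the sponsor's schedule. Only whether participants have started the product enters this projection; their pain ratings do not.

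Section 7.2 assumes that "there would be a mean improvement of 2 points on the Mankoski scale with a standard deviation of 5 points" and concludes that "a sample size of 68 patients would result in a 90% power to detect an improvement" with the paired t-test. It assumes that half of those enrolled will have a headache within 60 days, and says that 200 was "chosen to allow for various contingencies, including uncertainties in the assumptions and about compliance in this self-reported trial". It then refers back to the earlier text, stating that "the number 200 may be increased based on observed data concerning the number of participants with heartburn/indigestion", and leaves the re-estimation method to the SAP. Neither 97 nor a significance level appears in Section 7.

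In Section 7.1 the primary analysis population is those who consent, "report the onset of a headache, and have taken the study medication at least once".

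**The concern.** A reader who follows the reference from Section 5.1 to Section 7 finds 68 where 97 was promised, and Section 7.2 points back to Section 5.1. Each section leans on the other and neither gives a reason for 97. The removed pages lie outside Section 7, so they do not explain the gap.

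The number also drives a decision. It is the only trigger for raising the enrolment target, and the decision balances it against the sponsor's timelines. If 97 and 68 were rival targets, the choice between them would settle whether the trial is enlarged. If 97 were below what the stated power needs, the trial could stop too small. The mention of heartburn and indigestion in a headache protocol adds to the impression that Section 7.2 was carried over from another study without a full check.

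**Working it through.** **Inputs.** From Section 7.2: mean improvement 2, SD 5, paired t-test, 90% power, 50% of those enrolled with a headache. From Section 5.1: 97 treated, 200 enrolled. Assumed: two-sided 5%, because no level or sidedness is stated.

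**1. Reproduce the plan's 68.** The standardised effect is 2/5 = 0.4. Power comes from the noncentral t distribution with n − 1 degrees of freedom and noncentrality 0.4 × √n.

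- n = 67: power 89.7%
- n = 68: noncentrality 0.4 × √68 = 3.30, power 90.2%

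So 68 is the smallest n that reaches 90%. The normal approximation, ((1.960 + 1.282)/0.4)² = 65.7, agrees. At one-sided 5% the answer would be 55. The stated 68 therefore points to two-sided 5% (or, equivalently here, one-sided 2.5%), and an analyst can recover the missing level from the plan's own figures.

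**2. Is 97 large enough?** At n = 97 the noncentrality is 0.4 × √97 = 3.94 and power is 97.4%. If only some treated participants give a rating both before and after, 90% power needs 68 usable pairs, a share of 68/97 = 70.1%.

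**3. Does 97 fit the enrolment target?** 200 × 0.50 = 100 expected treated, just above 97. The threshold corresponds to a use rate of 97/200 = 48.5%. The two numbers sit together sensibly.

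**4. Can the basis of 97 be inferred?** On Section 7.2's effect and test:

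| Route | n |
|---|---|
| Two-sided 1%, 90% power | 97 |
| Two-sided 2.5%, 95% power | 97 |
| 68 with a 30% allowance for unusable data, 68/0.70 = 97.1 | 98 rounded up |
| Two-sided 5%, 97.5% power | 98 |

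The documents state none of these. The 30% route does not land cleanly on 97: 0.70 × 97 = 67.9, so 67 whole pairs, with 89.7% power. The basis stays unknown, and none of these should be supplied on the sponsor's behalf.

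**5. What would a shortfall cost?** Power at two-sided 5%, with pairs rounded down. The usable shares are assumed; the plan gives none.

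| Treated | 100% usable | 85% usable | 70% usable |
|---|---|---|---|
| 97 | 97.4% | 94.7% | 89.7% |
| 90 | 96.4% | 93.1% | 87.8% |
| 80 | 94.2% | 90.2% | 83.7% |

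This table needs Section 7.2's inputs, a significance level and a usable share. It does not need the reason 97 was chosen.

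**The case for a change.** The strongest case for acting is that 97 is the only criterion for enlarging the trial, and that the decision is a live one. With 200 enrolled and exactly 50% using the product, the binomial chance of at least 97 treated is 0.69, so there is about a 31% chance of falling short; for 68 the chance of falling short is negligible. Those who weigh 97 against the timelines ought to know what it protects. If it reflects a stricter significance level, that would also bear on the primary analysis, which tests three time points separately without a stated level. The repair costs only a sentence or two.

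Part of this stands. The reference is broken, and the sponsor's reason for 97 would be useful to have on file. The rest does not lead to a change. The rule can be operated as written, because 97 is stated plainly and used consistently. Choosing 97 over 68 makes enlargement more likely, which errs towards a larger trial. The projection ignores pain ratings, so the choice cannot steer the result. The cost of a shortfall can be computed without knowing the origin of 97. The 83.7% figure rests on an assumed 30% loss of pairs, and Section 7.2 itself calls its effect assumptions highly pessimistic.

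Even under the stricter levels, 97 complete pairs keep at least 90% power: 93.1% when 5% is split equally over three time points, and just over 90% at two-sided 1%.

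The heartburn and indigestion wording is a leftover. The next sentence of Section 7.2, and Section 5.1, both make clear that the count is of participants who have started the test product.

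**Conclusion.** The observation is accurate but calls for no change to the plan. Section 5.1 promises a description of 97 that Section 7 does not give, and the documents do not allow its basis to be inferred. What is missing is an explanation. A trial run as written aims for 97 treated against the 68 pairs its stated power needs, which is 97.4% power against 90.2%, with room for about 30% of treated participants to lack a usable pair. Supplying the reason would alter neither the target of 200, nor the trigger, nor any data or analysis.

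The conclusion rests on Section 7.2's mean of 2 and SD of 5 and on two-sided 5%, which the plan does not state but which its figure of 68 implies. It would weaken only if well under 70% of treated participants gave usable pairs, and the missing explanation has no bearing on that.
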